2.2 Procedure: Phase II (Aim 2- Intervention Development)

Creation of the Youth Community Advisory Board (YCAB) (N=9): Interventions that include stakeholders (in this case, YBMSM) in their development have the potential for increasing feasibility, acceptability and sustainability. Our YCAB will be made up of HIV-positive (by self-report) YBMSM who are willing to serve in an advisory capacity over the course of the project. We will form the YCAB, with nine individuals, within the first year of the Minority HIV/AIDS Research Initiative (MARI) award period to inform all subsequent phases of the research. We will aim to recruit a YCAB that is diverse in terms of socioeconomic status, educational attainment, and extracurricular interests. *Of note, given their intricate involvement in intervention development, members of the YCAB will be excluded from participation in the randomized control trial (Phase II).*

Time Commitment: Once membership is solidified, the YCAB will meet approximately every two weeks throughout the award period. We expect meetings to last between 2-3 hours on average, and they will be scheduled at mutually convenient times for the participants. YCAB members will be hired as temporary employees at Emory University and will be compensated for their time at a rate of \$12.50/hr.

Development of Social Capital Intervention: The development of our social capital-based intervention guidelines will require integrating scientific literature, preliminary data (both

qualitative and quantitative), and the perspectives of YBMSM, members of the YCAB, and other community and clinic-based stakeholders.

The development of the social capital intervention will continue throughout the first 18 months of the award period. Intervention development will be a continuous and iterative process during this timeframe and will involve [name], her mentors and collaborators, the study team and the YCAB. We will present qualitative and quantitative data from Phase I formative research to the YCAB as it is collected and analyzed as a way of “member checking” our results. We will also solicit ideas for the social capital intervention, discussing ideas in an iterative process until we have completed development of the intervention. Finally, we will have the YCAB test out a mock intervention with our team, and give us feedback on what works or does not work well in our curriculum. We will present the intervention to the YCAB as many times as needed in an iterative fashion until the study team and YCAB are satisfied with the final product. Our YCAB will give us input on every aspect of the intervention, including timing, location, content, and process. Before we are ready to share the intervention as part of our RCT, we will standardize the intervention in a standard operating manual which will also be reviewed by the YCAB.

The social capital intervention will be a group-level, multi-session program that entails a structured curriculum and process culminating in a community photovoice project. **The specifics of the community photovoice project are yet to be determined, and will be decided on with the YCAB as a part of the formative work.** The curriculum will also include components focused on training in advocacy, HIV knowledge, and project planning.

2.3 Procedure: Phase II and III (Aim 3- Randomized Controlled Trial) (n=120)

Randomized Controlled Trial Overview: We propose a prospective RCT in which groups of YBMSM will implement a novel intervention with the goal of enhancing social capital and engagement in care among YBMSM living with HIV. Sixty of our participants will be randomized to the treatment arm (divided into at least 6 groups) and participate in the social capital intervention, while the other 60 will be randomized to a group-based health promotion intervention (divided into at least 6 groups) that does not explicitly aim to build social capital (Health for life, or “H4L”). (See Figure 3) Each of the 6 groups in the treatment arm will implement the same intervention. Six groups are necessary in order to ensure that each group has no more than 10 individuals, ensuring that groups are neither too small nor too big. Each of the 6 groups in the group-based health promotion intervention arm will also complete the same curriculum. We will measure social capital using our Modified Social Capital Scale (MSCS; Appendix F, Section 2) at baseline, immediately after completing the intervention (approximately 1 month) and at 4 and 10 months after beginning the intervention. We will also abstract clinical data from electronic medical records at these time points in order to quantify any effect on our care engagement outcomes.

Overview--Intervention Arm: The social capital intervention will be implemented according to the detailed guidelines and manual developed in Phase I above. We will plan for our intervention (and our control condition) to be delivered in either a one day or consecutive two day group meeting at Emory University Rollins School of Public Health or another agreed upon location, at mutually convenient times for the participants. Staff members will be flexible in case evening or weekend meeting times are more convenient for the study participants. The exact number of sessions and

format of the intervention may be modified based on YCAB input; it may be that the intervention can be delivered in fewer sessions, or in a retreat format, to enhance acceptability and retention.

Community Photovoice Project: Our social capital intervention will focus on developing skills and group-work that culminate in participant-derived ***photovoice projects***. This is based on our own and others' prior qualitative work that demonstrates HIV-positive YBMSM's interest in HIV education, peer mentoring, and community involvement.^{48,49} We envision having six sets of intervention and control groups with 10 YBMSM in each group (Figure 3). *Each group of YBMSM will be encouraged to complete a 30 day photovoice challenge.* The 30 day challenge is based on a prior community action project done as a part of our CFAR-funded research, which was a Photovoice project conducted by [name] and an MPH student.⁵⁰ Photovoice is a participatory action research methodology in which groups of individuals from a population of interest are given cameras to document events, people and places of significance in their lives.⁵¹ In that project, n=7 YBMSM were recruited from AID Atlanta (one of our CBO partners) and given digital cameras with which to document and describe events, people and places of significance in their lives. Their pictures and the ensuing discussions gave us insight into community and identity within the population. Costs included digital cameras, compensation for transportation to meetings, and printing of photos for display in a booklet and a community exhibit.

As we saw preliminarily with our Photovoice experience, we expect that the process of working together with other YBMSM and engaging the community will enhance the social capital of individuals in the intervention arm by creating bonds that will lead to the aforementioned health-promoting mechanisms: informational support, emotional support, instrumental support and collective efficacy (Figure 2).

Again, the exact nature of the 30 day challenge and the intervention will be determined in conjunction with the YCAB over the course of Phase I intervention development. (The control groups will not participate in the 30 day challenge). The process of working on the 30 day challenge as part of the proposed social capital intervention has the potential to increase bonding social capital through the group's interactions with one another, as well as bridging social capital through meaningful connections with community partners and study staff. Finally, the act of creating and executing a community-oriented project will also increase participants' sense of collective efficacy (as measured by items in the MSCS), another important component of social capital.

Overview--Control arm: The control arm will participate in a health education intervention that will be delivered in a group, but without a specific goal of creating group cohesion or social capital. The intervention will be a modified version of "Health for Life" or H4L, which was used as a control arm intervention in a recently completed protocol of the Adolescent Trials Network which was co-chaired by [name] (University of Michigan). This intervention was specifically developed for young MSM of color and focuses on general health topics including diet, exercise, and safe sex. Details about the Health for Life program are included as Appendix G. We will modify the H4L intervention as needed based on the input of our YCAB. Similar to the intervention arm, the control participants will participate in either a one day or a consecutive two day group meeting at a convenient time and location. The exact number of sessions and format of

the intervention may be modified based in YCAB input; as with the intervention arm--it may be that the intervention can be delivered in fewer sessions, or in a retreat format, to enhance acceptability and retention. The same format and number of sessions will be used for both the intervention and control arms.

Procedures for intervention and control participants:

Tokens of appreciation: We will provide participants with two gift cards (value \$75) as a token of appreciation for their time and will also provide Metropolitan Atlanta Rapid Transit Authority passes (MARTA cards; \$5 fare for a single round-trip) if needed for transportation assistance. \$25 will be given on the first day and \$50 will be given on the second day

Retention Plan: Our previous experiences have demonstrated the need to pay careful attention to participant retention: part of the role of the study staff is to remind participants about intervention sessions and study visits, scheduling, and discussing any issues they face in the trial procedures. In [name] ongoing work with the Metropolitan Atlanta Community Adolescent Rapid Testing Initiative (MACARTI) trial, these procedures have resulted in at least an 87% retention among participants who were primarily HIV-positive YBMSM (and may be higher as the follow-up period has not yet ended).

Clinical Outcome Measures: Viral load values and appointment attendance will be extracted from the participants' electronic medical records (EMR). The goal is to abstract measures that correspond to the 0 month (baseline) and 10 month (long term follow-up) time points at which participants will be completing surveys. However, we recognize that lab tests (CD4, VL) in the clinical setting may not necessarily be conducted at a time that corresponds to the survey time point. In light of this limitation, and to make the procedures more uniform, we plan the following: (1) the baseline viral load will be the most recent measurement preceding study participation. If this is >6 months prior to the date of enrollment, this will be considered a missing value. (2) The 10 month viral load will be the first value drawn on or after the date that is exactly one year from the beginning of study participation. If this test is done >6 months after the target date, it will be treated as a missing value.

Study visits: In addition to attending the intervention sessions, participants in both arms will be asked to come to the IDP clinic or Rollins School of Public Health to participate in three study visits: One at baseline before starting the intervention (0 months), immediately after completing the intervention (around 1 month), 4 months and a long term follow-up at 10 months after study completion. The main purpose of these visits will be to complete a survey to measure any change in social capital between the pre- and post-intervention periods. The survey (Appendix F) will also include measures of other theoretically relevant constructs including depressive symptomatology, stigma, and social support. We will also verify the participants' most recent medical care facility and obtain medical record release forms to facilitate abstraction of data on engagement outcomes. Participants will receive tokens of appreciation for each completed study visit (\$25 for the first visit and \$50 for the second) and given MARTA cards at these visits.

Follow-up qualitative interviews: We will conduct n=30 qualitative in-depth interviews in Year 4 with a subset of interested participants who were enrolled in the social capital intervention arm, in order to understand their experiences in the program and solicit feedback for future implementation of the intervention. Procedures and analytic plans will be as described in the Phase 1 interviews above. Participants will sign a separate informed consent to participate, and will receive an additional \$25 token of appreciation for their time if they choose to do so. The maximum total amount for tokens of appreciation for participants who do all sessions is \$175.

2.4 Audience and stakeholder participation: Our study follows a community-based participatory approach designed to ensure stakeholder participation. First, we will conduct interviews with community stakeholders to inform our understanding of social capital in our target population. Second, we will create a youth community advisory board (YCAB) designed specifically to engage members of the community at each step of the process. Finally, at the end of the project, we will plan to disseminate findings not only in academic publications but also in a community forum.

2.5 Description of risks (physical, social, psychological, economic, other) to individual or group: Risks to participants from a physical standpoint are minimal, as there are no medical procedures being conducted in this study. There are risks from a social and/or psychological standpoint, primarily related to the potential for a breach of privacy which could lead to inadvertent disclosure of HIV status or sexuality. One source of such a breach could be study records; we will take the necessary precautions to prevent this including password protection of all participant records and de-identification of datasets before analysis. A second source of such a breach is other participants, as the activities include involvement in a group project with other HIV-positive individuals. We will make sure to explicitly discuss privacy concerns and instruct participants not to disclose others' participation and/or HIV status; however this will be impossible for us to enforce. We will ensure that participants are aware of this potential risk in the informed consent process.

2.6 Description of anticipated benefits to the research participant: If our intervention is effective, it will provide direct benefits to the participants in terms of improved social support, social capital and HIV related outcomes. Those in the control arm should also receive the benefits of a health education intervention that will improve their knowledge about HIV and other health issues.

2.7 Emergency care: Given the non-invasive nature of this study, it is not expected that involvement in either the control or treatment arm would lead to any physical or psychiatric emergencies. However, were an emergency to occur during the course of involvement, study staff would be instructed to contact the PI immediately via cell phone or pager. [name] would then direct the participant to either the ER (including Grady Psychiatric Emergency Services if applicable) or their primary medical provider, and she would also record the adverse event for immediate reporting to the Emory IRB (Adverse Event form in Appendix H).

2.8 Study time line:

Activity	Pre-Award	Year 1	Year 2	Year 3	Year 4
Research Activities					
Team consolidation, hiring new staff, planning					
Development of project guidelines/SOPs					
IRB review: Emory, Grady					
IRB review/project determination review: CDC					
Qualitative interview guide development					

Aim 1: IDIs with YBMSM												
Aim 1: IDIs with CBOs, providers												
Aim 1: Qualitative analysis												
Aim 1: Statistical analysis of survey data												
Aim 2: YCAB formation												
Aim 2: Intervention development												
Aim 3: Enrollment and follow-up of control arm												
Aim 3: Enrollment and follow-up of intervention arm												
Aim 3: Data analysis from pilot intervention/follow up												
New R01 application												

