3.7 Consent Process: In order to screen potential participants for eligibility for the RCT, we will obtain online consent – this will be accompanied by a verbal consent discussion of the consent document if a staff member is present (e.g., at a community event or in the clinic), and will be online only if a participant is self-referring to the eligibility survey from a flyer or friend. For the RCT participants, we will obtain written consent. The consent form is attached and includes specific permission to access participants' medical records for the purposes of abstracting the clinical outcomes (Appendix B). We are requesting a waiver of written consent for the IDI participants (YBMSM as well as key informants) as their signing of the consent form would be the only written record of participation and therefore could increase potential for breach of confidentiality. There is precedent for such waivers in our prior research; furthermore, federal regulations state that the IRB may waive the requirement for written consent if this will be the only record linking the subject and the research, and the principal risk would be potential harm resulting from a breach of confidentiality (45 CFR 46.117(c)). We will obtain verbal consent using the scripts attached to this application (Appendix A). YCAB members will not consent as they are not technically research participants, but rather advisors to the research process.

3.8 Tokens of Appreciation:

In Phase I, participants (whether YBMSM or key informants) will receive \$50 cash or gift card for participating in in-depth interviews. Participants in the RCT will receive \$25 cash/gift card for the first intervention session and \$50 for the second intervention session. Also, they will receive \$25 for taking the social capital surveys at 4 months and 10 months after study completion (\$150 total). The subset who participate in post hoc qualitative interviews will receive an additional \$25 for that visit and therefore receive a total of \$175 over the course of 10 months participating in the study. Participants who refer up to 5 potential participants to the study will receive \$10 for each participant that enrolls in the study (Up to \$30). Additionally, MARTA cards (valued at \$5/round-trip) will be offered to all participants in all phases to enable them to get to the study sites and participate.

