Psychological Distress	Brief Symptom Inventory	53	Phase III: RCT participants at 0, 4 and 10 months

Outcome Measures: The primary outcome measure will be social capital. The core measure of social capital that we will use is our Modified Social Capital Scale (MSCS) described above, which we developed and validated exclusively with YBMSM. Our aim is to discover whether social capital improves as a result of being in the social capital intervention, and also to see if there is any similar effect in the control arm. Secondary outcomes will be measures of HIV care engagement, namely: (1) Retention in care, (2) Adherence to medications, and (3) HIV viral load suppression. As per Institute of Medicine (IOM) recommendations, **retention in care** will be measured by determining, within the 10 months of the study period, (a) participation in continuous care, that is, at least two or more routine HIV visits at least three months apart, (b) receiving two or more CD4 tests, and (c) receiving two or more viral load tests.⁶⁰ **Adherence to antiretroviral medications** will be measured using a composite of single item self-report question and pharmacy refill records. **HIV viral suppression** will be considered achieved if the medical records report a viral load below the level of detection for the site-specific assay. Viral load values and appointment attendance will be extracted from the participants' EMR.

4.3 Intervention Content: As the details of the intervention will be influenced greatly by the formative research and the input of the YCAB, it cannot be described in full detail at this time. The main intervention delivery will consist of either a one day or a consecutive two day group

meeting among the YBMSM with time divided between health education and community photovoice project planning. Each group will contain ten YBMSM; we plan for six groups each in the control and intervention arms. As detailed above, the intervention will consist of a group-based curriculum in program planning and HIV education, culminating in the planning and implementation of a community photovoice project.

4.4 Outcomes: The primary outcome of interest for the RCT will be social capital, as we are aiming to determine whether or not our intervention is effective in increasing social capital. We will also look at engagement outcomes, to determine whether or not increasing social capital has an impact on care engagement in our participants.

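### The ten-month viral load is taken from month 12 onward, so it cannot match the ten-month survey it is meant to accompany

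*Combined protocol and SAP*

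**What the plan says.** Section 2.3, Clinical Outcome Measures, gives the purpose of the chart abstraction: "The goal is to abstract measures that correspond to the 0 month (baseline) and 10 month (long term follow-up) time points", meaning the survey dates. It accepts that clinic laboratory tests may not fall on survey dates and sets two rules to make the procedure uniform.

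- Baseline: "the baseline viral load will be the most recent measurement preceding study participation", missing if more than 6 months before enrollment.
- Follow-up: "The 10 month viral load will be the first value drawn on or after the date that is exactly one year from the beginning", where the clock starts when the participant joins the study. The rule then limits how late a result may be: "If this test is done >6 months after the target date, it will be treated as a missing value". The target date is not defined separately.

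Other sections place the last assessment near month 10:

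- The 2.3 overview puts the last survey 10 months after the intervention begins, with chart abstraction at the survey time points.
- Section 5.2 (Data collection) puts the last survey 10 months after enrollment and chart extraction at baseline and 10 months.
- Table 2 in section 4.2 lists viral suppression at baseline, post-intervention and 10 months.
- The retention definition in section 4.2 is counted "within the 10 months of the study period" and includes "receiving two or more viral load tests".
- Section 3.8 describes payments "over the course of 10 months participating in the study".

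No section explains the one-year anchor.

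**The concern.** The label and stated aim say ten months; the operating rule says one year. Section 2.5 states that the study carries out no medical procedures, so viral load comes only from routine clinic testing and a skipped result is not replaced by a study sample. A participant tested at month 10 or 11 has that result passed over for a later one, or has a missing outcome if no later test falls in the window. The baseline rule has no comparable gap, because it accepts values right up to the start of participation.

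Viral suppression is one of three named secondary outcomes, and section 4.4 uses the engagement outcomes to ask whether raising social capital affects care. That question is better served when the survey score and the viral load refer to about the same time. As written, retention describes months 0 to 10 and suppression describes a later period.

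There is also a practical risk. Staff who abstract charts at month 10, as section 5.2 literally says, would find no eligible value. Others may use the value nearest month 10 because of the label. The choice would then be made at abstraction, case by case.

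**Working it through.** The plan gives no figure to reproduce, so the check is calendar arithmetic in months from the start of participation. It assumes that participation, enrollment and the intervention start on the same date.

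**Inputs**

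- Window opens: month 12 (2.3, Clinical Outcome Measures).
- Window closes: target date + 6 months (same place).
- Last survey: month 10 if counted from the start of the intervention (2.3 overview) or from enrollment (5.2). Section 2.0 gives 9 months after completion; with completion at about month 1, this is 1 + 9 = 10. Study visits in 2.3, and section 3.8 ("for taking the social capital surveys at 4 months and 10 months after study completion"), give 1 + 10 = 11.

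**Window and lag**

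Lag = window limit − survey month.

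| Target date read as | Window | Lag, survey at month 10 | Lag, survey at month 11 |
|---|---|---|---|
| One-year date | 12 to 12 + 6 = 18 | 2 to 8 | 1 to 7 |
| Ten-month date | 12 to 10 + 6 = 16 | 2 to 6 | 1 to 5 |
| For comparison: rule opening at month 10 | 10 to 10 + 6 = 16 | 0 to 6 | – |

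The first row is the natural reading, since the one-year date is the only date that the rule names. Under both readings of the current rule the window opens at month 12, so no value from months 10 to 12 qualifies.

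**How many participants have a test in the skipped interval (illustration)**

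Assume evenly spaced tests every T months with random phase. The plan does not give T. T = 5 is the spacing of two tests in ten months (10/2), the minimum count in the retention definition.

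- Share with a test in months 10 to 12 = 2/T.
- Mean lag after a month-10 survey, for T ≤ 6: 2 + T/2 under the current rule (window 12 to 18), T/2 under a month-10 target.

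| T (months) | Share 2/T | Of 120 | Mean lag, current rule | Mean lag, month-10 target |
|---|---|---|---|---|
| 3 | 67% | 80 | 3.5 | 1.5 |
| 4 | 50% | 60 | 4.0 | 2.0 |
| 5 | 40% | 48 | 4.5 | 2.5 |
| 6 | 33% | 40 | 5.0 | 3.0 |

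**Missing values**

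With windows of 18 − 12 = 6 and 16 − 10 = 6 months, the expected missing share is the same under both rules: none for T ≤ 6, and 1 − 6/T for T > 6 (25% at T = 8, 50% at T = 12). On this reading the current rule loses extra data only if testing stops or the care facility changes after month 10.

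**The case against.** Six points can be made for the plan.

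1. *The target date is undefined, so months 12 to 18 is one reading.* This is true. Under the other reading (months 12 to 16) the window is 4 months wide and the missing share is 1 − 4/T for T > 4: 20% at T = 5 and 33% at T = 6, against none with a 6-month window. The statement that missingness is equal therefore depends on the first reading. Both readings exclude months 10 to 12, and the ambiguity is a further reason to rewrite the rule.

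2. *The ten-month period in section 4.2 defines retention only, and the phrase in 3.8 concerns payment. Neither limits chart follow-up, and retention and suppression need not overlap.* This stands: non-overlap alone is not an error. The fault is the conflict with the correspondence that section 2.3 sets as its goal.

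3. *The counts rest on an assumed test interval, even spacing and complete ascertainment.* This also stands. They show who could have a skipped test, not whose suppression status would change. No bias between arms has been shown.

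4. *Charts are retrospective, so the rule implies a later look.* This is fair. The ten-month extraction in 5.2 may be only a label, and the timeline bars in 2.8 are not readable. The abstraction date is a less certain point than the window itself.

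5. *The consent form may already permit later chart access.* Its wording is not available for this review. Sections 2.3 and 5.2 do obtain record releases and check the care facility at survey visits, the last of them near month 10, so access after that needs confirming.

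6. *The plan already accepts imperfect timing.* It does, and that supports an allowance around month 10. It does not explain opening the window two months late.

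**Conclusion.** The concern holds and should be fixed. Section 2.3 contradicts itself, and its rule conflicts with the ten-month timing in the 2.3 overview, Table 2 and section 5.2. On the natural reading the viral load comes from months 12 to 18, which is 2 to 8 months after a month-10 survey (1 to 7 if the survey falls at about month 11). The mean lag is 2 months longer than under a month-10 target for any regular test interval up to 6 months.

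The consequence is limited to the secondary viral suppression outcome. The primary social capital outcome is untouched, and the rule applies equally to both arms. The window follows from the plan's own dates, given a common start date and the one-year date as target. The shares and counts of skipped tests are illustrative.

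**What to change.** Choose one of two definitions before outcome data are examined:

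- **Ten-month outcome.** Set the target to the ten-month date and keep the 6-month allowance: the first value in months 10 to 16. This fits the stated goal. It is still forward-only, so a value drawn just before month 10 is not used.
- **One-year outcome.** Keep months 12 to 18, relabel the outcome as one-year, and drop the claim that it corresponds to the ten-month survey.

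With either choice:

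- Define the target date explicitly.
- State that the final chart abstraction takes place after the window closes, and confirm that record releases cover that period.
- Make the 2.3 overview, Clinical Outcome Measures, Table 2 and the 5.2 extraction entry agree.

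Two useful side items are a phone or email check for a change of care facility, using the contact database in section 5.4, and a single survey origin in place of the after-completion wording in 2.3 (Study visits) and 3.8.

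The cost is wording, one dated chart pull and, if adopted, one short contact. No tests or visits are added. Compared with a pull at month 10, data for the last participants arrive 16 − 10 = 6 months later, or 18 − 10 = 8 if the one-year outcome is kept. Compared with the existing month-18 limit, the ten-month option closes 2 months earlier. A participant who changes care after the last visit may need a new signed release; without access the value would be missing.
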